Tai Chi Chih: TCC and other mind-body interventions are directed toward combining aerobic exercise with stress-reduction and structured mindful cognitive approaches that add to improvement in mood and self-esteem. TCC is also known as a "CHI- generating mindful exercise.⁷⁷ The search for the mechanisms of change has focused on two components, relaxation and exercise. In a meta-analysis on the effects of relaxation training, Hyman et al. found that various relaxation response-based interventions led to a reduction of somatic symptoms with additional effects on symptoms of anxiety and depression,⁷⁸ blood pressure,⁷⁹ and recovery from immune-mediated diseases.^{78,80} *As observed in our pilot,⁸¹ TCC in combination escitalopram, appears beneficial for enhancing treatment in LLD, an approach that may readily incorporated into future clinical practice.* Comparing a Chi-generating exercise (TCC) to a comparable non-chi generating exercise is innovative and may shed light on the difference between the two in clinical outcomes (mood, health functioning and quality of life), and the underlying mechanism.

Longitudinal design and long-term follow-up: The goals of behavioral and drug therapies for depression are to improve depressive symptoms and induce remission, thereby preventing relapse and recurrence.^{5,82,83} Remission rates in clinical trials of antidepressant drugs in older adults are around 30-35%.⁸⁴ Extended treatment trials are necessary to optimize interventions for depressive symptoms in older adults.^{85,86} Hence, we propose to use a 12-week acute treatment trial to also satisfy the TCC training objectives. Follow-ups at 6 and 12 months will evaluate maintenance of response/remission or depression relapse (or 24 months if 12 months have passed). Notably, very few studies designed to establish the mechanisms of treatment response in the elderly have included extended follow-up.

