Health and Wellness Education (HEW) control group: This condition will serve as an active control for nonspecific treatment elements such as attention and group support that pose rival explanations for the effectiveness of TCC. Participants will be informed that this intervention is designed to help reduce the severity of depressive symptoms, and all participants will be offered a choice of TCC in the end of the interventions, to balance expectations for the TCC intervention; therefore, reducing the placebo effect. The PI and trained study staff will implement HEW using a manual that will present educational information and describe learning objectives and patient activities to promote integration of material. The detailed protocol for Health Education has been developed and used in the pilot project. The HEW sessions will be held once a week for 60 minutes over the 12-week treatment period. We will follow a didactic format, inviting experts to lecture on key topics, followed by focused group discussion, and post-discussion self-help quizzes to assess patient learning. This novel use of a non-exercise control intervention, which matches the exercise intervention in duration, frequency and social contact, represents an important methodological advance.¹⁴³ Participants will be instructed to practice at home in computer searches addressing the health topics discussed in the session for 20 minutes per day. Weekly supervision by [name] with project health education instructors will be used to monitor instructors’ adherence to the educational protocol. Tai Chi Chih trainers will follow the same manual. We will contact Tai Chi Chih Association for an opportunity to monitor TCC trainers’ adherence to the manual protocol. Participants will be asked to keep diaries of exercise or computer searches and the adherence will be compared between the groups.

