6.2 Description of Evaluations

Primary outcome measures will include efficacy evaluations using the 24-item HAMD¹¹⁰ to quantify mood symptoms. **Secondary outcome measures** will include the Clinical Global Impression-Severity and Improvement scale (CGI)¹²² to quantify overall severity and clinical improvement over time (2 min). In addition, we will administer the Montgomery Asberg Depression Rating Scale (MADRS)- commonly administered in geriatric depression that is easily comparable to other trials, and the Geriatric Depression Scale (GDS),¹²³ a self-assessment scale often used in geriatric depression trials (10 min).

Measures of comorbid neuropsychiatric symptoms will include the Hamilton Anxiety Scale,¹¹³ a widely used measure of anxiety symptoms (10 min), the Apathy Evaluation Scale (AES),¹¹¹ a measure of the severity of apathy (15 min), and the Unified Parkinson's Disease Rating Scale (UPDRS)¹²⁴ used for the assessment of psychomotor slowing and extrapyramidal symptoms (10 min). Pittsburgh Sleep Quality Index (PSQI) is an 18 item self-report measure of subjective sleep quality (5 min).¹²⁵

Measures of medical comorbidity will include the Stroke Risk Factor Prediction Chart (SRF)^{126,127} of the American Heart Association for rating cerebrovascular risk factors (5 min) and the Cumulative Illness Rating Scale-Geriatric (CIRS-G)¹²⁸ used for rating the severity of chronic medical illness in 14 organ-systems (15 min). *Health-Related quality of life and physical functioning* will be determined using the Medical Outcomes Study Short Form 36-Item Health Survey (SF-36),¹²⁹ that records health-related quality-of-life, mental, physical, and social functioning (15 min), the Connor-Davidson Resilience scale (CD-RISC), as a measure of stress coping ability¹³⁰(5 min), the Quality of Life Enjoyment Scale (Q-LESS-Q),¹³¹ a brief assessment instrument of life satisfaction commonly used in clinical trials of psychiatric populations including the elderly (5 min). Pain assessment has been also included as a measure of self-rated pain to monitor any changes in the pain severity over time (5 min) We will also include a self-reported physical activity record for monitoring physical activity in both groups (3 min).¹³²

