6.2.3 Blinding

We have considered different options for blinding/masking procedures. We will provide treatment groups that both incorporate “exercise and wellness education,” which we believe will generate equal expectations for benefit. Both groups will be informed that they will receive exercise and education upon consent and entry into the study. Each group will have an option of trying and switching to the two other interventions after up to 24 months of follow up, which facilitates blinding and controls for the exercise effect. For ethical reasons, we cannot have a “usual care” group in which older depressed subjects at high risk for worsening of depressive symptoms in the absence of behavioral treatment. All subjects will be blind to the fact that symptomatic, functional and cognitive improvement are the outcomes of interest, and the differences in the interventions, since all participants will be recruited to receive a “wellness and exercise treatment program.”

Blind Assignment: The trained behavioral raters will also be “blind” to the treatment assignment.

Both statisticians and the PI will be blind to the group assignment. Only trainers and study coordinators will be unblinded, but they will not have access to the data monitoring or analyses. Database staff entering the data or managing the data will be blind to the treatment assignment. Groups in the documentation will be identified as 1 and 2. If unblinding occurs in the process of assessment, we will assign different raters who will continue to be unaware of the treatment group, and will re-establish reliability on all assessment instruments. We will minimize potential “placebo effects” by balancing expectations by introducing two “wellness and exercise” interventions for depression. We will measure and compare the expectancy for the outcomes at baseline, Week 12, Month 6 and Month 12 as specified below (or Month 24 if 12 months have passed). Both classes will be taught by different instructors. We will control for the “instructor” effect if several instructors teach classes.

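### The plan claims to control for exercise, but HEW contains none, so a Week 12 difference can be credited to the TCC package and not to its chi or meditative component

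*Combined protocol and SAP*

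**What the plan says.** The protocol gives two incompatible accounts of the comparator.

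**Comparator as exercise.** Section 6.2.3 (Blinding) says of the participants: "Both groups will be informed that they will receive exercise and education upon consent and entry into the study". It adds that the option of "switching to the two other interventions after up to 24 months of follow up" is a feature that "facilitates blinding and controls for the exercise effect". Section 2.2 (Study Rationale, Tai Chi Chih paragraph) says: "Comparing a Chi-generating exercise (TCC) to a comparable non-chi generating exercise is innovative", and suggests that the trial may shed light on how the two differ in outcome and mechanism.

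**Comparator as education.** Section 5.1 describes HEW as follows: "This novel use of a non-exercise control intervention, which matches the exercise intervention in duration, frequency and social contact". On class content it says: "We will follow a didactic format, inviting experts to lecture on key topics". Group discussion and quizzes follow, and the homework is computer searching on health topics. Sections 2.1 and 5.1 give HEW's purpose as control for attention and social or group support.

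**Measurement.** Section 6.2 promises: "We will also include a self-reported physical activity record for monitoring physical activity in both groups". The schedule in Appendix A, as supplied, has no row for this record. It has a row for homework diaries at Weeks 2 to 12 and one for therapeutic expectations.

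**The concern.** A reader of Sections 2.2 and 6.2.3 would conclude that exercise is balanced between the arms, so that a TCC advantage reflects something beyond physical activity. Section 5.1 removes the basis for that conclusion. If the text stands, a positive result could be reported as controlled for exercise when it is not.

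Two further matters follow. First, HEW participants who were told to expect exercise will find none in class, while knowing that TCC is to be offered later. Section 6.2.3 relies on equal expectations to limit placebo effects, so the inaccurate description works against its own purpose. Second, the instrument that would describe the activity difference in a common unit is promised in the text but absent from the schedule.

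**Working it through.** The plan gives no figure for exercise exposure, so there is none to reproduce. The check rests on the prescribed practice and on a comparison of sections.

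**1. Prescribed movement, 12 weeks.** Inputs: TCC class 60 minutes once a week and home practice 20 minutes a day (Section 5.1); 12 weekly classes (Section 6). Home practice is taken as 7 days a week.

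- TCC: 60 + 7 × 20 = 200 minutes a week; 200 × 12 = 2,400 minutes = 40 hours.
- TCC without the 10-minute warm-up and 5-minute cool-down in each class: 45 + 140 = 185 minutes a week; 185 × 12 = 2,220 minutes = 37 hours.
- HEW: lectures, discussion, quizzes and computer searches, so 0 hours.

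Assigned exercise is an exact multiple of the arm indicator. A model with an intercept, arm and assigned exercise has rank 2 with 3 columns, so the data cannot separate an effect of assigned exercise from an effect of arm.

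**2. Timing of the stated control.** The primary analysis in Section 9.6 assesses the treatment effect at 12 weeks. The switch in Section 6.2.3 comes after up to 24 months of follow-up. An event after the endpoint cannot control for exposure before it.

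**3. What the activity record could add.** Total activity, unlike assigned exercise, varies within both arms. Suppose full adherence, equal arms and a between-person SD *s* of background activity, which the documents do not give. The share of variance in weekly activity explained by arm is then R² = (200² × 0.25) / (200² × 0.25 + *s*²).

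- *s* = 60 minutes a week: 10,000 / 13,600 = 0.74.
- *s* = 300 minutes a week: 10,000 / 100,000 = 0.10.

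The overlap with arm would thus be partial. Activity is measured after randomization, however, so adjusting for it would not give a randomized estimate of the chi or meditative component. Its use is descriptive.

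**4. Section 6.2 against Appendix A.** Section 6.2 names 15 rating scales, questionnaires and records outside the cognitive battery: HAMD, CGI, MADRS, GDS, Hamilton Anxiety, Apathy Evaluation, UPDRS, PSQI, stroke risk, CIRS-G, SF-36, CD-RISC, Q-LES-Q, pain and the activity record. The first 14 have a row, reading the CVRF row as the stroke-risk chart; the activity record does not. Section 9.5 has a general sentence on the timing of outcome measures, but it does not name this record. No model in Section 9 uses physical activity.

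**5. Diaries as a substitute.** Section 5.1 first describes diaries of daily exercise, then diaries of exercise or computer searches. In HEW a diary entry may therefore be search time, so time in practice (Sections 9 and 9.6) is not clearly an exercise measure common to both arms.

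**The case against.** The strongest reply is that this is a wording conflict and not a design flaw. Aim 1 and Hypothesis 1 ask only whether TCC does better than HEW. No hypothesis in Section 1 and no contrast in Section 9.6 separates chi or meditation from movement, and an education control matched on contact is a legitimate choice. This stands. A reader might infer from the complete overlap of arm and assigned exercise that the primary comparison is biased. It is not: randomization protects the comparison of TCC as a package with HEW.

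A reader might also infer that unequal expectations will inflate the HAMD difference. The documents do not show that. HAMD is scored by blinded raters (Sections 6.2.3 and 6.2.4). Credibility and expectation are rated after the second session and post-intervention (Section 5.2), and expectancy is compared through follow-up (Section 6.2.3 and Appendix A). The later offer of TCC is itself meant to balance expectations. These measures would reveal an imbalance. They would not prevent one, and HAMD still draws on what the patient reports.

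Nor do the documents support saying that activity will go unrecorded. Appendix A is not exhaustive: concomitant medication at each visit (Section 5.3) and the repeat physical examination at Week 12 (Section 6) have no row either. Section 10.1 cites an assessment schedule in an Appendix B that is not in the supplied text. The diaries may capture some exercise, and other mind-body practice must be reported at visits (Section 5.3). What stands is that Appendix A as supplied omits the record although the other Section 6.2 scales have rows.

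Finally, consent pages were not available, so what participants are told is known only from Section 6.2.3.

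**Conclusion.** The point holds as a contradiction that should be corrected. The design does not have the control for exercise that Sections 2.2 and 6.2.3 state. The prescribed contrast is about 40 hours of movement (37 without warm-up and cool-down) against 0 over 12 weeks, assuming full adherence and daily home practice. That figure measures exposure; it is not an estimate of bias in HAMD.

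The consequence is limited to attribution. A Week 12 difference would support TCC as a package over education matched for time and attention. It would not show that chi or meditation, rather than movement, produced the benefit. The primary model, the power calculation and the validity of the randomized comparison are unaffected. Telling HEW participants that they will receive exercise is inaccurate on the protocol's own description, and its effect on expectations is plausible but not demonstrated.

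The conflict may be left over from a design with a further arm. Section 2.2 twice refers to two control conditions, and Section 6.2.3 mentions two other interventions, although the trial has two arms in all. That origin is an inference.

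**What to change.** 1. Reconcile Sections 2.2, 5.1 and 6.2.3. Delete the claim that switching controls for exercise and the description of the comparator as a non-chi exercise. In the same edit, remove the references in Sections 2.2 and 6.2.3 to two control conditions and two other interventions.
2. State that the comparison is the TCC package versus time- and attention-matched education, and that conclusions will not separate chi or meditation from physical activity.
3. Correct the statement that both arms receive exercise wherever participants are given it, for example by describing a program of either exercise or education.
4. Add the Section 6.2 activity record to Appendix A at baseline, Week 12, Month 6 and Month 12/24, and report it descriptively by arm. Section 6 limits the Month 12/24 visit to MRI participants, so the last collection would cover only them.

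The cost is a text amendment, a change to participant information, a 3-minute form the protocol already names, and a narrower mechanistic claim. Randomization, sample size and the primary analysis do not change.

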6.2.4 Follow-up Visits

Follow-up Assessments: Assessments of efficacy and safety will take place approximately every 2 weeks for the remaining weeks of the 12 week trial, followed by naturalistic monthly follow-up from **4-6 months**. All follow-up visits, except those at 3, 6, and 12 months- will last for about 30 min. Due to the nature of our population of older adults who may forget their appointments or have competing medical appointments some flexibility in scheduling will be allowed with the interval (+/-) 1 full week of the expected week throughout the study.

Similarly, longer assessments at months 3, 6, and 12 may be split into to 2 visits to accommodate clinical, neuropsychological, MRI and laboratory assessment (at 3 and 12 months). The MADRS, HAM-D, and GDS are to be obtained once between the baseline and screening visits, but re-administered at baseline if the baseline visit occurred significantly after the screening visit for 2 months or later. If participant is unable to complete at Month 12, this follow-up will be completed at Month 24.

We will assess home practice and adherence, safety and medications at each assessment visit. The visit frequency will serve as an additional safeguard to monitor worsening of depression, and the emergence of side-effects or suicidal ideations. All behavioral outcome assessments will be identical in both groups and performed by the trained raters blind to the treatment assignment (*Table 2*).

6.2.5 Completion/Final Evaluation (will be scheduled within a window of +/- 1 week in regards to the week of the final class)

The follow-up visits at 3, 6, and 12 months will last 1.5-3 hours for outcome measures.

Visit 10-11 at week 12: A physical, psychiatric examination, and a follow-up blood draw and MRI for peripheral biomarker analysis will be repeated.

Visit 14-17 at 6 and 12 months - will reassess primary and secondary outcomes and the remission/relapse status.

Remission at 12 weeks / 6 and 12/24 month follow-up: Subjects who achieve remission by week 12 will be followed monthly to detect relapse of major depressive episodes. The goal of continuation treatment is to ensure stability of response/remission, and to optimize coping, cognition, physical functioning and life satisfaction. We will explore the predictors and biomarkers of relapse for future studies. We will continue to monitor safety monthly by phone and in-person at 6 and 12 months, when relapse of depression will be documented. If participant is unable to complete within the Month 12 timeframe, this will instead be followed during the Month 24 timeframe.

6.2.6 COVID-19 Questionnaire and Assessment

We will also instill a COVID-19 Questionnaire to all active participants to ensure optimal safety reporting and to correlate with current psychiatric measures. This will be administered as a survey, with the responses coming verbatim from the participant. We will also remotely administer HAMD, HAMA, and MADRS at the same time point. This visit will only be administered once, but will happen as soon as possible once approved, and will be a visit separate from the rest of the scheduled portions of the study.

7.2 Methods and Timing for Assessing, Recording, and Analyzing Safety Parameters

Safety Evaluations: Safety will be assessed at each visit. All subjects will receive an initial *medical evaluation* including a complete physical examination with neurological and neuropsychiatric examinations, electrocardiogram (ECG) (for potential cardiac complaints), and laboratory testing to rule out new-onset medical illnesses that could account for behavioral and cognitive symptoms. *All abnormal physical or laboratory findings will be reported to subjects' primary physicians with subject's consent. If abnormal physical or laboratory results are considered responsible for depression, the subject will be excluded from participation.* All subjects will be interviewed about their recent history of psychiatric and medical illnesses, psychosocial stressors, current

medications and health status. In addition, vital signs including pulse rate, systolic blood pressure, and body weight will be obtained at each visit. The UKU Side Effect Rating Scale,¹³⁷ a comprehensive rating scale for monitoring adverse events in clinical trials, will also be completed at all follow-up visits.

7.3 Adverse Events and Serious Adverse Events

An **adverse event (AE)** is defined as any unfavorable and unintended diagnosis, symptom, sign (including an abnormal laboratory finding), syndrome or disease which either occurs during the study, having been absent at baseline, or if present at screening/ baseline, appears to worsen. Adverse events are to be recorded regardless of their relationship to the study intervention.

NOTE: Changes in the primary and secondary outcome measures (e.g. depression) will not be considered side-effects but will be monitored as outcome variables.

A **serious adverse event (SAE)** is generally defined as any untoward medical occurrence that results in death, is life threatening, requires inpatient hospitalization or prolongation of existing hospitalization, results in persistent or significant disability/incapacity, or is a congenital anomaly.

All severe adverse events will be reported to the subjects and to their primary physicians and the UCLA IRB/ DSMB committee within one week of PI's awareness, and within two weeks to the NIH.

- If a patient demonstrates worsening of their depressive symptoms by week 12 (i.e., CGI-I score > 4) of treatment, they will be discontinued from the study and referred for appropriate clinical services.
- Suicidal ideations with the HAMD item 3 score of 3 or greater

All dropouts will be analyzed by the reason for termination and the reasons will be classified as:

- a) Lack of efficacy; b) Side-effects; c) Lost-to-follow up; d) Hospitalization; e) Death; f) Other
- Relation to the study interventions: a) likely; b) probable; c) unlikely.

7.4 Reporting Procedures

We will arrange for **Data Safety Monitoring Committee** meetings at approximately six month intervals. The DSMC will consist of one external and one internal member, [name], an expert geriatric psychiatrist, [name] a geriatrician, and a statistician- methodologist [name]. All DSMC members have considerable experience in geriatric clinical issues. The DSMC will meet at least once every six months to review study progress. Members of the committee agree to keep all information confidential. Those members of the investigative group that are involved with the treatment and assessment of patients within the study will not review data that involve the comparison of outcomes (i.e., adverse events, treatment response, remission, etc.).

The Board will also issue a report annually to the PI and the IRB. The board will review summaries of the study progress to ensure that consent documentation is properly obtained and stored. They will also review progress in filling subject recruitment ethnic requirements. They will also determine whether study coordinators and investigators are collecting and organizing data properly. Key personnel will provide progress reports to facilitate this review. The board will also review any recent research relevant to the study. The summary reports will provide data on enrollment and adverse events. Adverse events will be monitored using the UCLA Adverse Event and/or Incident Reporting forms (Forms HS-5 & HS-6). Additional support for these activities will be provided by the CTSI of the UCLA School of Medicine, which appointed Associate Dean,

[name], and a full-time staff member, [name]., to assist in data safety monitoring in all protocols administered through the CTSI. A committee consisting of at least four medical school faculty members will review the findings of the DSMC and make recommendations for additional action as needed.

Assessment and monitoring of suicidal risk will occur **at each visit and by phone between visits**. We have applied the standard procedures that are required and approved by the UCLA Institutional Review Board. We have employed the same procedures in our ongoing studies of late-life depression since 1995, and have had no suicide attempts among our subjects. We will monitor suicidal ideations using the third item of the Hamilton Depression Scale during each visit to the site. Monitoring for SI will be done at each visit independent of the outcome assessment. The blind rater will be instructed to inform the PI of scores ≥ 3 . [name] will be available for "on call" consultations to address concerns of worsening of suicidal ideations. He will also participate in the review of the dropouts due to suicidal ideations and other causes during DSMB meetings. Subjects with active suicidal ideations with or without a plan, HAMD-24 score ≥ 3 , will be excluded from participation. We will call subjects between visits to monitor suicidal ideations. We will encourage participation of their family members in the study who will be encouraged to call the patient and the study staff in case suicidal ideations emerge during the study. In the presence of persistent suicidal ideations, subjects will be discontinued from the study and referred to clinical services or to the community for treatment.

